Hospitalization does not include rehabilitation facilities, hospice facilities, respite care (i.e., caregiver relief), skilled nursing facilities or homes, routine emergency room admissions, or same day surgeries (as outpatient/same day/ambulatory procedures). Hospitalization or prolongation of hospitalization in the absence of a precipitating, clinical AE/SAR is not in itself an SAE/SSAR.

Unanticipated Problems (UPs)

An UP is an incident, experience, or outcome that specifically causes increased risk to the study or to its participants which may be of medical or non-medical etiology, and meets the following criteria:

1. Unexpected (in terms of nature, severity, or frequency), given (a) the research procedures that are described in the protocol-related documents, such as the IRB-approved research protocol and informed consent document; and (b) the characteristics of the subject population being studied
2. Definitely, probably, or possibly related to participation in the research (i.e., there is a reasonable possibility that the incident, experience, or outcome may have been caused by the procedures or materials involved in the research); and
3. Suggests that the research places participants or others at a greater risk of harm (including physical, psychological, economic, or social harm) than was previously known or recognized
4. All UP reporting will follow the same guidelines as noted above for SAE/SSAR reporting, and must include a corrective action plan/measures to prevent recurrence.

Reporting by Principal Investigator

For all events (AE/SAR and SAE/SSAR), monitoring and reporting to the PI or EC begins at the time that the participant provides informed consent, which is obtained prior to the participant's participation in the study, i.e., prior to undergoing any study related procedure and/or receiving study supplement, through and including 30 calendar days after the subject completes the study. Events should be recorded on the Adverse Event electronic case report form (eCRF). Do not delay the initial reporting of an event in order to obtain resolution or follow up information.

For all events, the PI must pursue and obtain adequate information both to determine the severity and causality of the event. For events with a causal relationship to the study supplement, follow-up by the Investigator is required until the event or its sequelae resolve or stabilize at a level acceptable to the PI, who concurs with that assessment.

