In the rare event that the PI does not become aware of the occurrence of a SAE/SSAR immediately (i.e., if an outpatient study subject initially seeks treatment elsewhere), the PI is to report the event within 24 hours after learning of it and document the time of his/her first awareness of the event.

Severity Assessment

The Common Terminology Criteria for Adverse Events (CTCAE), version 5.0, for detailed descriptions of Severity Grades has been used in this study. The CTCAE schema is classified by body system and event using the Medical Dictionary for Regulatory Activities (MedDRA) System Organ Classification (SOC) hierarchy and provides descriptions of events that qualify under each severity rating. The CTCAE v5.0 schema was accessed from

https://ctep.cancer.gov/protocolDevelopment/electronic_applications/docs/CTCAE_v5.0.xlsx and

[figure not shown]
https://ctep.cancer.gov/protocolDevelopment/electronic_applications/docs/CTCAE_v5_Quick_Reference_5x7.pdf.

The following table contains general descriptions of Adverse Event Severity Grades.

Please note: Grade 1 (Mild) AE/SARs are not entered in the electronic CRF.

CTCAE Severity Grading Scale

Severity Grade	Description
1	Mild. Asymptomatic or mild symptoms; clinical or diagnostic observations only; intervention is not indicated.
2	Moderate. Minimal, local, or non-invasive intervention indicated or limiting activities of daily living (i.e. preparing meals, shopping for groceries/clothes, managing money, using telephone, etc.)
3	Severe or medically significant but not immediately life-threatening. Hospitalization or prolongation of hospitalization indicated OR disabling OR

	limiting self-care (e.g. bathing, dressing, feeding self, using toilet, taking medications, etc.)
4	Life-threatening consequences; urgent intervention indicated.
5	Death. Death related to adverse event.

Notice that severity and seriousness are different concepts. For example, a headache may be severe (interferes significantly with subject's usual function) but would not be classified as serious unless it met one of the criteria for SAE/SSARs.

Causality Assessment

The study nomenclature for assessing the causal relationship between the study supplement and an event is listed in the following table.

Adverse Event/Suspected Adverse Reaction Relationship to Study Supplement

Unrelated	No temporal association to study supplement An alternate etiology has been established.

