The DSMB will use a combination of, notifications, event specific reports, and scheduled cumulative trial reports to keep the EC and the IRB informed about real and potential safety issues.

Notifications

Notifications are comprised of an email to the EC and DSMB with available information on the date and nature of the event, the study physician’s evaluation of the severity, expectedness, and relatedness to study supplement; and the assessment of the event given the information known at the time of the initial reporting.

Event Specific Reports

Event specific reports are formal written reports providing the details of the event (including circumstances surrounding the event, laboratory testing, concomitant medications, and any formal diagnoses made via medical intervention). These reports include a full assessment by

the study physician of the severity, expectedness, and relatedness to study supplement as well as any available status update on the participants.

Scheduled Cumulative Trial Reports

Scheduled cumulative trial reports will be prepared semi-annually by the study PI. These will be used by the DSMB to assess recruitment, subject safety, and continued trial feasibility. These reports include total numbers of AE/SARs and SAE/SSARs experienced in the overall trial. The information provided includes both new events reported since the last DSMB meeting and cumulative events reported during the life of the trial.

CTU Reporting Requirements to DSMB and IRB

Once the event has been reported to the PI or the study physician, it will be reported to the Executive Committee within 48 hours. The UofL CTU (part of the EC) will use the Medical Dictionary for Regulatory Activities (MedDRA) System Organ Classes (SOC) to classify all AEs/SARs (including SAEs/SSARs assessed by PI or study physician). Additional supporting documentation may be requested from the PI and study team to enable the UofL CTU to accurately assess the event for reporting.

Reportable Events:

All unexpected events, all events related to study product, and all events with a severity grade of 3 or higher are reported by the UofL to the DSMB and the IRB.

Reporting Timeframe:

[figure not shown]
For events which are unexpected AND associated with study supplement, the CTU will notify the IRB and DSMB within 72 hours of learning of the event; with an event specific report filed no later than 7 days post notification.

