The events listed below will follow the same reporting criteria for SAE/SSARs as it relates to the PI as well as the CTU and are to be considered sufficient to halt the study procedure. If subject develops any of the following conditions within 48 hours of planned supplement consumption, study supplement delivery will be halted in that particular participant:

[figure not shown]
1. Diarrhea / Vomiting / Stomach Upset
2. Sudden drop in blood pressure
3. Sudden drop in blood sugar
4. Hemodynamically unstable

Holding Rules

The expected number of SAE/SSARs in this trial is anticipated to be too small to support formal statistical stopping rules. However, the following criteria are provided as guidelines under which this **clinical trial may be put on hold pending a detailed investigation by the DSMB**. The assessment of the event shall include the relationship to the trial procedures as unrelated or possibly related. If possibly related, an indication of causality to a specific aspect of the study supplement / procedures will be determined: (e.g. study supplement consumption related, study supplement safety related, study supplement manufacturing related).

Holding Criteria

The DSMB will recommend putting the trial on hold as soon as it is notified of **one or more of holding criteria** listed below. The study holding criteria have been created under the guidelines of current literature data and the 21 CFR code of the FDA regulatory information. The study holding criteria:

1. 20% or more cases of out of the total enrollment with Diarrhea / Vomiting / Stomach Upset
2. 20% or more cases of out of the total enrollment with Sudden drop in blood pressure
3. 20% or more cases of out of the total enrollment with Sudden drop in blood sugar
4. 20% or more cases of out of the total enrollment with Hemodynamically unstable events
5. 20% or more cases of out of the total enrollment with Hospitalizations
6. Or any other reason specified by the DSMB, study EC, bulk supplier or manufacturing pharmacist

As soon as any of the above is identified, the EC will inform the IRB and the DSMB. In addition, the DSMB will monitor the distribution of all SAE/SSARs, and the PI will be responsive to all DSMB concerns regarding SAE/SSARs that are not part of holding criteria listed above.

In addition, the DSMB may also recommend stopping the trial for the performance-related issues that would prevent the study from meeting its scientific objectives, such as:

[figure not shown]

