The cumulative number of grade 3 or 4 toxic events will be monitored after each person is enrolled ⁴⁸. If the cumulative number of toxic events produces enough evidence to conclude that the true toxicity rate is greater than or equal to 33% ($Pt_0 = 0.33$) then the trial will be stopped early for safety reasons. If the cumulative number of toxic events after person is treated is greater than or equal to the associated boundary value b_i then the combination supplementation is rejected for safety considerations (monitoring table with these boundaries will be generated using Ray and Rai, 2011)⁴⁸. With this rule, there is only a 5% chance of stopping the trial early for lack of safety if the true toxicity rate is less than 33%. Continual assessment of the toxic events ensures we do not expose an undue number of participants to a harmful supplementation.

A second sub-analysis to be executed is the effect of Carnosine supplementation in participants with cardiovascular disease compared to the effect of Carnosine supplementation in participants without any cardiovascular disease.

Subgroup Evaluations

The effect of subgroup stratum on the relationship between carnosine supplementation and the endpoints (both primary and secondary) will be assessed. If a carnosine supplementation effect is demonstrated, it is not likely to behave identically among all important subgroups. The subgroups of interest are age, sex, race, socioeconomic status, diabetes, smoking, hypertension, and cardiovascular disease risk scores.

These additional analyses can sometimes be helpful in identifying extreme differences in the effects of supplementation among subgroups, although the literature wisely warrants that caution be used in interpreting subgroup analyses.

Additional Analyses

We will use the 6 week and 12-week EPC levels to assess the change of EPCs from baseline to 6 weeks and 12 weeks, assessing if this trajectory is related to carnosine supplementation using mixed model analysis of variance.

We will evaluate the relationship among the indices of the primary endpoint – EPCs. Specifically, we will assess the relationship between the differences in EPCs, adjusting for important baseline covariates.

[figure not shown]
Multiple Comparisons

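### The Section 15 toxicity boundary counts only grade 3 or 4 events, so a death with no earlier graded report falls outside it; the count should be grade 3 or higher and should name the carnosine arm (minor)

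*Combined protocol and SAP*

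**What the plan says.** Section 15, Monitoring Toxic Supplementation (Safety), sets a continuous boundary on a cumulative count: "The cumulative number of grade 3 or 4 toxic events will be monitored after each person is enrolled". The trigger is worded "If the cumulative number of toxic events after person is treated is greater than or equal to the associated boundary value", and crossing it rejects the supplementation. The threshold rate is 33%, and the stated error is that "there is only a 5% chance of stopping the trial early for lack of safety if the true toxicity rate is less than 33" per cent. The boundary values are not given; the plan says that a table will be generated by a cited method.

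Section 13, Severity Assessment, adopts CTCAE version 5.0. Grade 4 is life-threatening, and grade 5 is a separate level: "Death. Death related to adverse event". Section 14, Reportable Events, uses the inclusive form: "all events with a severity grade of 3 or higher are reported" to the DSMB and the IRB.

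The Section 15 paragraph names no arm. It speaks of persons enrolled, then treated, and of a combination supplementation, although this trial has no combination.

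**The concern.** A rule meant to stop a harmful supplement should count the worst outcome on the scale that it uses. As worded, the boundary stops at grade 4. Section 14 includes grade 5 when it defines reportable events, so the two sections do not match, and nothing elsewhere adds deaths to the boundary count.

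The gap is narrower than it first looks. Section 13 tells the investigator: "Do not delay the initial reporting of an event in order to obtain resolution or follow up information". An event first reported as grade 3 or 4 that later proves fatal may therefore already be in the count. What drops out is a fatal event with no earlier grade 3 or 4 report.

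The unnamed arm is a second, smaller gap in the same paragraph. If the count took in both arms, placebo participants would dilute the rate compared with 33%.

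**Working it through.** **Inputs from the documents.** Threshold 33% and stated error 5% (Section 15); 200 participants per arm (Section 11, Carnosine Supplement and Placebo Supplement); death is grade 5 (Section 13).

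**Assumptions.** The documents give no boundary values, expected toxicity rates or death rate. I assume one otherwise uncounted death per 200 participants, 1/200 = 0.5 percentage points, and two boundary shapes for n = 200, checked after every participant by exact recursion.

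**The plan's 5%.** It cannot be reproduced without the boundary values, but it is attainable, so it is not shown to be wrong.
- Flat shape: b_k is the smallest r with P(Bin(k, 0.33) ≥ r) ≤ 0.0068. This gives 13/20, 26/50, 46/100 and 84/200; overall stopping probability 4.98% at a true rate of 33%.
- Constant-excess shape: b_k = ceil(0.33k + 1.96 × √(200 × 0.33 × 0.67)) = ceil(0.33k + 13.03). This gives 20/20, 30/50, 47/100 and 80/200; overall 4.80%.

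**Effect of leaving out grade 5.** Chance of stopping at grade 3–4 rate p, then at p + 0.5 points:

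| Grade 3–4 rate | Flat | Constant-excess |
|---|---|---|
| 5% | 0.00004% → 0.00006% | below 0.00001% in both cases |
| 20% | 0.071% → 0.083% | below 0.00001% in both cases |
| 30% | 1.57% → 1.88% | 0.55% → 0.83% |
| 40% | 49.7% → 54.8% | 62.9% → 68.1% |

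The change reaches about 5 points only at a 40% rate, where the chance of stopping is already about half or more.

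**Effect of the unnamed arm.** With 200 per arm, the pooled rate is (c + p)/2, for carnosine rate c and placebo rate p, whatever the boundary. Setting (c + p)/2 = 33% gives c = 66% − p. With assumed placebo rates of 0%, 5% and 10%, carnosine would have to reach 66%, 61% and 56% before the pooled rate met the threshold.

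**The case against.** *Deaths are not invisible.* A reader might infer that deaths could accumulate unmonitored. The documents do not support that. Every event of grade 3 or higher goes to the DSMB and the IRB. The first notice is due within 72 hours if the event is unexpected and associated with the supplement, and within 15 days otherwise. Holding criterion 6 in Section 14 lets the board act for any reason it specifies. A count boundary set at 33% is also not the means by which a single death would stop this trial. This stands and keeps the point minor. It does not remove the mismatch: death is not among the numeric holding criteria, and criterion 6 is discretionary.

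*The text already points to carnosine.* Section 15 speaks of supplementation being rejected and of harmful supplementation. Section 8, Sample Size Recommendation, labels the two groups supplementation and placebo. Usage is mixed, because Section 11 also describes a placebo supplement, but the lean is towards the active arm. The pooled tallies elsewhere, "These reports include total numbers of AE/SARs and SAE/SSARs experienced in the overall trial" and "20% or more cases of out of the total enrollment with Hospitalizations", belong to the semi-annual reports and the holding criteria, not to this boundary. A reader might infer from them that the 33% rule will be run on both arms together. That is possible, but it is not what the plan says, and the pending table may settle it.

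*A pooled count would not leave gross harm unchecked.* Assumed rates of 50% on carnosine and 5% on placebo pool to (50 + 5)/2 = 27.5%. With the flat shape, a carnosine-only count stops with probability 99.6% and a pooled count of 400 with 0.05%. It is tempting to conclude that such harm would go unstopped. However, Section 14 calls for a hold at 20% of total enrollment in any one listed category, including hospitalization, and Section 13 describes grade 3 partly as hospitalization being indicated. If the events fell mainly in one category (an assumption), 27.5% would exceed that limit. With 5% on placebo, the pooled rate reaches 20% once carnosine reaches 35%, since (35 + 5)/2 = 20. At 35%, even the carnosine-only flat boundary stops only about 11% of the time. The DSMB also knows allocation and can see an imbalance between arms. No document suggests rates near these: Section 14 expects too few serious events to support formal stopping rules.

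**Conclusion.** The grade wording is a definite, minor error: the boundary omits the top grade of the protocol's own scale and does not match the protocol's own reporting rule. This conclusion rests on the text alone. The effect on stopping is very small under both assumed boundary shapes, and the other routes to the DSMB limit the practical consequence. The stopping probabilities are illustrative, because the boundary values, the death rate and the toxicity rates are not in the documents.

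The unnamed arm is an ambiguity to close, not a shown error. The averaging result needs only equal arms, but whether any dilution would occur depends on a pooled reading that the text does not favour.

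**What to change.** In Section 15, Monitoring Toxic Supplementation (Safety), change the count to events of grade 3 or higher (grades 3 to 5). In the same edit, state that the count and its denominator are treated participants in the carnosine arm. Generate the boundary table on that basis. The 33% threshold need not change.

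The cost is a wording edit to one paragraph. It needs no extra data and no extra participants. It needs no added step for the Randomization Committee and no new unblinding, because the DSMB is already unmasked and already receives every event of grade 3 or higher.

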Sample Size Computations and Assumptions

The primary outcome measures are EPC-2, EPC -3, EPC -4, EPC -7, and EPC -8. Also, there are many secondary outcome measures. Based on our pilot study, mean and SD (standard deviation) are reported below.

	EPC-2	EPC-3	EPC-4	EPC-7	EPC-8
Mean	0.675783	0.016016	0.050813	0.297092	0.631728
SD	0.702561	0.010805	0.056709	0.412414	0.691299

This is a longitudinal study and primary observations will be made at baseline, 6 weeks and 12 weeks follow-ups. Due to 5 primary outcome measures, we adjusted alpha=0.01 (=0.05/5). Due to multiple sub-studies, we plan to enroll a large evaluable cohort of size n=240. With a correlation of 0.5 on any two consecutive time-point measures, (this is a conservative estimate) and n1=120, n=120 at alpha= 0.01 and power=0.90, we can detect the effect size of 0.5 SD using a two sample t-test in a longitudinal setting. The detectable effects for each EPC is given below.

Power	Correlation	EPC-2	EPC-3	EPC-4	EPC-7	EPC-8
80%	0.50	0.351	0.005	0.028	0.206	0.346
90%	0.50	0.223	0.003	0.018	0.131	0.219
80%	0.80	0.197	0.003	0.016	0.116	0.194
90%	0.80	0.156	0.002	0.013	0.092	0.153

To adjust for attrition/drop out we have increased the sample size to 400.

Associations of PM_{2.5} exposures with measured outcomes will be estimated using mixed effects models. We will use interaction variables to detect whether the association between PM_{2.5} and outcomes is significantly different between with or without carnosine groups. We will perform a formal mediation analysis, which allows for interactions to determine the degree to which carnosine levels mediate the effect of PM_{2.5} on our outcomes. Plots of subject-specific differences over pollution concentrations along with regression plots will be generated.

Sample Size Recommendation

Sample size of 240 participants (120 carnosine supplementation, 120 placebo group) provides sufficient sample size for the primary endpoint as well as other secondary endpoints.

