Due to the prolonged intervention period (12 weeks), two follow-up visits and the inconvenience of taking multiple oral capsules daily, we anticipate a 40% attrition from screening (Visit # 1) through 12-week follow-up (Visit # 4). Therefore, we have established a goal of stratified identification of a total of 400 participants (1:1) at screening (Visit # 1). We anticipate that with a conservative estimate of 60% retention, 120 participants in each group (supplementation, placebo) will complete the entire study.

Multiple Testing Issue

Type I error correction in the context of an early phase clinical trial that performs multiple tests can serve to protect the study interpretation against Type I error inflation. However, the use of corrections for multiple comparisons in “proof-of-concept-studies” is problematic. At this investigational level, tight control of the overall family-wise Type I error rate would increase the likelihood that the investigators would miss a finding of potential importance by attributing it to chance simply because the p-value is large. The study investigators have, in this protocol, attempted to balance the need to control the number of evaluations with the need to identify new effects by not incorporating a multiplicity correction. The primary outcomes measures will be declared significant for alpha <0.01. There will not be any adjustments for secondary outcome measures and will be declared significant at alpha <0.05.

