There are 5 primary endpoints: difference in EPCs (EPC-2, EPC-3, EPC-4, EPC-7, and EPC-8) between Carnosine and placebo groups at 6 weeks and 12 weeks. These endpoints will be evaluated at the alpha=0.01. There are four secondary endpoints: difference in EPCs between Carnosine and placebo groups at 12 weeks, difference in EPCs between Carnosine and placebo groups at 6 weeks, difference in arterial stiffness between carnosine and placebo groups at 6 and 12 weeks, difference in endothelial microparticles between carnosine and placebo groups at 6 and 12 weeks, and difference in platelet monocyte aggregates between carnosine and placebo groups at 6 and 12 weeks.

Continuous variables will be presented by summary statistics (such as mean, median, standard error, range, 95% CI, correlations) and the categorical variables by frequency distributions (frequency counts, percentages and 95% CI). We will also calculate correlations along with confidence intervals. To identify significant differences due to intervention, we will compare the differences using a two sample t-test. We will use regression (logistic or linear) to model and test the effect of other covariates such as age and race. We also will compare outcome measures using GLM and MIXED model procedures to account of repeat observations. General statistical analyses will be performed with the SAS statistical software package (SAS Institute Inc., Cary, NC).

Statistical Monitoring Rule

[figure not shown]
Safety monitoring of the accumulated outcomes data is designed to ensure the continuing safety of the currently enrolled participants and participants not yet enrolled. This is achieved by stopping the trial early to reduce the number of participants exposed to a harmful or ineffective supplementation.

Monitoring Non-efficacious Supplementation (Futility)

We do not plan any interim analyses for futility due to longer follow-up (1 year).

Monitoring Toxic Supplementation (Safety)

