In this study, no adjustments have been made for multiple comparisons. Measures of effect will be effect size, the standard error of the effect size, the 95% confidence interval for the effect size and the *p*-value. *P*-values will be interpreted at nominal 0.05 levels.

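### The five primary EPC endpoints are set at 0.01 in three places but read at nominal 0.05 under Multiple Comparisons, and the 6- and 12-week EPC differences are listed as both primary and secondary

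*Combined protocol and SAP*

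**What the plan says.** **Threshold of 0.01.** Section 8, Sample Size Computations and Assumptions, divides 0.05 by the five primary outcomes to reach 0.01. With 120 per arm and 90% power it then says that "we can detect the effect size of 0.5 SD using a two sample t-test in a longitudinal setting". Section 8, Multiple Testing Issue, describes a balance struck "by not incorporating a multiplicity correction. The primary outcomes measures will be declared significant for alpha <0.01", and continues: "There will not be any adjustments for secondary outcome measures and will be declared significant at alpha <0.05". Section 15, Primary and Secondary Endpoints, says of the five primary EPC endpoints: "These endpoints will be evaluated at the alpha=0.01".

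**Threshold of 0.05.** Section 15, Multiple Comparisons, says "In this study, no adjustments have been made for multiple comparisons" and that p "values will be interpreted at nominal 0.05 levels". It makes no exception for the primary endpoints.

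**Role of the EPC comparisons.** Section 15, Primary and Secondary Endpoints, defines the primary endpoints as "difference in EPCs (EPC-2, EPC-3, EPC-4, EPC-7, and EPC-8) between Carnosine and placebo groups at 6 weeks and 12 weeks". It then announces four secondary endpoints and names five, two of which are the EPC differences at 12 weeks and at 6 weeks. Section 5, Study Design, puts the 12-week EPC difference among the secondary endpoints. The endpoint list later in section 5, the objectives in section 6 and Study Endpoints in section 8 all place both visits in the primary endpoint and list no EPC as secondary.

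**The concern.** Two rules exist for the same five endpoints. One spends 0.05 across them; the other spends 0.05 on each. Section 8, Multiple Testing Issue, contains both ideas in adjoining sentences, because it disclaims a multiplicity correction and then states the corrected level.

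The dual listing is a second, separate route to the same problem. Even if Multiple Comparisons were read narrowly, an EPC difference at 6 or 12 weeks with p = 0.03 would miss 0.01 as a primary endpoint and pass 0.05 as a secondary one. Correcting only one of the two passages leaves the other route open.

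What is at stake is the error control that the 0.01 was introduced to give: a report could call a primary EPC significant at a level for which the trial was not designed.

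**Working it through.** **Inputs.** From section 8, Sample Size Computations and Assumptions: five primary EPCs, alpha 0.05/5 = 0.01, 120 per arm, 90% power, 0.5 SD, correlation 0.5 between consecutive measurements, pilot SD of EPC-2 0.702561. Two-sided testing is assumed, since sidedness is not stated. Correlations between EPCs are assumed.

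**1. Which alpha does the sample size rest on?** The SD of change is SD × √(2(1 − 0.5)) = SD, so levels and changes share one calculation.
- Normal formula: n per arm = 2(z₁₋α/₂ + z₀.₉₀)² / 0.5².
- At 0.01: 8 × (2.576 + 1.282)² ≈ 119.1, so 120 per arm. This is the plan's figure.
- At 0.05: 8 × (1.960 + 1.282)² ≈ 84.1, so 85 per arm.
- One-sided 0.01 would need 105 per arm, so the match supports the two-sided assumption.
- Power at 120 per arm from the noncentral t (238 df, noncentrality 0.5/√(2/120) = 3.873): 89.8% at 0.01 and 97.1% at 0.05.

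The stated design corresponds to 0.01.

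**2. Which results are decided differently?** Those with p between 0.01 and 0.05. The boundaries are t × √(2/120), with √(2/120) = 0.1291.
- 0.05: 1.970 × 0.1291 = 0.254 SD.
- 0.01: 2.597 × 0.1291 = 0.335 SD.
- For EPC-2 with the pilot SD: 0.179 to 0.236.
- If 200 per arm were available at a visit (the number to be randomized, hence the ceiling): 0.197 to 0.259 SD.

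**3. Family-wise error over five EPCs.**

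| | at 0.01 | at 0.05 |
|---|---|---|
| Upper bound, 5 × alpha | 5% | 25% |
| Independent, 1 − (1 − alpha)⁵ | 4.9% | 22.6% |
| EPC correlation 0.5 (assumed, simulated) | 4.2% | 18.3% |
| EPC correlation 0.8 (assumed, simulated) | 3.0% | 12.8% |

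The difference between the columns is the chance, with no effect on any EPC, that none reaches 0.01 but at least one reaches 0.05: 22.6 − 4.9 = 17.7 percentage points if independent, and 12.8 − 3.0 = 9.8 at correlation 0.8.

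**4. If each visit were tested separately and either could count.** There would be 5 × 2 = 10 tests. At 0.01 the upper bound is 10%. With independent EPCs and a correlation of 0.5 to 0.67 between the two visits' change scores, simulation gives 9.1% to 8.7%. At EPC correlation 0.8 it gives 5.5% to 5.2%.

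**5. The wording on visit and method.** The sizing names the two-sample t-test. Section 15 uses that test to identify differences due to the intervention and adds GLM and mixed models as further comparisons; the mixed model of the EPC trajectory sits under Additional Analyses. The lead method can thus be inferred. No section says whether the test applies to week 6, week 12 or a combination of the two.

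**The case against.** The best defence is that the intended rule is clear. Three statements specific to the primary endpoints give 0.01, and Multiple Testing Issue sets out the full scheme: primary at 0.01, secondary unadjusted at 0.05. Multiple Comparisons is generic, names no endpoint and follows Subgroup Evaluations and Additional Analyses, so it may have been written for those. This stands as a reading of intent, and the sizing supports it. It does not remove the conflict, because the sentence speaks of the study as a whole.

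On roles, a coherent scheme can be built: a longitudinal primary comparison per EPC with single-visit contrasts as secondary. Section 5, Study Design, partly fits it, since the change across both follow-up visits comes before the secondary list. That section also names exactly four secondary endpoints, without EPCs at 6 weeks, so the fifth item in section 15 may be an editing leftover. But no section states this scheme, and the 6-week level comparison in section 5 does not fit it.

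A reader might infer that the analysis method is wholly open. The documents do not support that, because the two-sample t-test is tied to the 0.01 in the sizing and leads in section 15. A reader might also infer that the plan already commits to ten primary tests. It does not say that the visits are tested separately or that either suffices.

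**Conclusion.** The plan is wrong as written on two points. The significance threshold for the primary EPCs is stated inconsistently, and the 6- and 12-week EPC differences hold two roles with different thresholds. The first is a conflict of wording that the sample size already resolves in favour of 0.01. The second leaves the visit or combination of visits carrying the 0.01 undefined.

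The consequence is mainly one of false positives. Reading all five EPCs at 0.05 lifts family-wise error from at most 5% to 22.6% under independence, or about 13% at an assumed EPC correlation of 0.8. The zone of 0.254 to 0.335 SD assumes 120 per arm with either a single-visit level or a change score at correlation 0.5. The figure of about 9% for ten tests at 0.01 is conditional on separate testing of both visits and on independent EPCs.

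The documents do not show that the sponsor intends to test the primary EPCs at 0.05, and that should not be inferred.

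**What to change.** 1. In section 15, Multiple Comparisons, limit the no-adjustment and nominal-0.05 statements to secondary and exploratory analyses. In section 8, Multiple Testing Issue, limit the clause disclaiming a multiplicity correction in the same way. Keep 0.01 for the five primary EPCs.
2. Give each EPC comparison one role, worded identically in section 5 (Study Design and the endpoint list), section 6, section 8 (Study Endpoints) and section 15. Either remove the 6- and 12-week EPC differences from the secondary list, or state that they cannot support a claim for a primary EPC that misses 0.01. Correct the count of secondary endpoints to match.
3. Before unblinding, state which visit or combination of visits carries the 0.01 for each EPC. If both visits are to be tested separately and either may count, 0.01 does not guarantee 5% over ten tests and the level must be set again.

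Item 1 is wording only. Items 2 and 3 need a decision but no added visits, participants or data; naming a single visit would change the endpoint as most sections now state it. The downside is that a primary EPC result with p between 0.01 and 0.05 can no longer be called significant.
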